**PASS Information**

Title	Pregnancy outcomes in Multiple Sclerosis populations exposed and unexposed to interferon $\beta$ – a register-based study in the Nordic countries
Protocol version identifier	ER-9430
Date of last version of protocol	18 August 2015
EU PAS register number	Study not yet registered, to be registered.
Active substances	Interferon (IFN)- $\beta$ -1a (L03AB07) IFN- $\beta$ -1b (L03AB08)
Medicinal products	Avonex, Betaferon, Extavia, Plegridy, Rebif
Procedure number	Avonex: EMEA/H/C/000102 Betaferon: EMEA/H/C/000081 Extavia: EMEA/H/C/000933 Plegridy: EMEA/H/C/002827 Rebif: EMEA/H/C/000136
Marketing authorization holder(s) (MAH)s	Avonex, Plegridy: Biogen Idec Ltd Betaferon: Bayer Pharma AG Extavia: Novartis Pharma AG Rebif: Merck Serono Europe Ltd
Joint PASS	Yes
Research question and objectives	The overall research question of this study is to determine if exposure to IFN- $\beta$ s before or during pregnancy has an adverse effect on pregnancy outcomes in patients with Multiple Sclerosis (MS) including, as requested by the Committee for the Medicinal Products for Human Use (CHMP), the identification of the prevalence of adverse pregnancy outcomes in women with MS unexposed to IFN- $\beta$ products.
Countries of the study	Finland (FIN) Norway (NOR) Sweden (SWE)
Author	[name], EPID Research, [name] Email: [contact] [contact]

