#### **Prescription Registers (FIN, SWE, NOR)**

Information on maternal MSDMD exposure before and during pregnancy will be obtained from the Prescription Registers based on reimbursed drug purchases (information is linked to DPP in FIN). The Prescription Registers contain information on outpatient medication purchases in pharmacies (established FIN 1994, SWE 2005, NOR 2004). Prescription-only medicines are only sold in pharmacies, and dispensing requires a prescription issued by a physician or a dentist in FIN, SWE and NOR. In FIN, the register contains information on all purchased prescribed medicines that are reimbursed by the government. This excludes, for instance, most contraceptives. In SWE and NOR, all prescribed medicines purchased in community pharmacies are included irrespective of reimbursement status. The prescription data in the registers includes patient's ID, the generic name of the drug, ATC code, the brand name, the formulation and package, the amount as the defined daily dose (DDD), the date of purchase, the prescribing practice (primary vs. secondary healthcare), and the prescribing physician's area of specialisation.

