## Drugs and Pregnancy Project (FIN)

DPP will be a data source for the Finnish data regarding information on maternal MS diagnosis, MSDMDs, TOPFAs, live births, stillbirths, and MCAs. The purpose of the Finnish DPP, initiated in 2003, is to evaluate the pattern of drug use during pregnancy and estimate the effect of drug use on pregnancy outcomes. The research data are based on information obtained from the Finnish national health registers: the MBR, the Register on Induced Abortions and the Malformation Register, all maintained by THL (Artama et al. 2011). Information on maternal drug use and drug reimbursements is obtained from the Prescription Register and the Register on Reimbursed Medications, both maintained by the SII. The research database enables evaluation of the frequency and type of maternal drug use during pregnancy retrospectively from the year 1996 onwards (at the time of data extraction until the end of 2014). Drug purchases are recorded covering a time period from one month prior to pregnancy to the end of pregnancy in the DPP.

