#### **Exposure to any teratogenic medications (including steroids):**

Information on co-medication will be obtained from Prescription Registers (FIN, SWE, NOR). The medications included consist of high-risk medicines during pregnancy according to the Swedish Catalogue of Approved Drugs (FASS) (Berglund 1984, FASS 1993). This classification comprises 4 separate categories (A, B, C, D): A includes the safest drugs; B is divided into 3 subgroups (B1, B2, B3); and C and D categories are used for drugs which may have different risks for the foetus depending on the evidence on which the risk is based. In this study, drugs from categories C and D will be included as potentially teratogenic drugs or teratogenic drugs (see Annex 3 for the classification of teratogenic medications and for a detailed list of specific ATC codes). From these medications a binary variable will be created to indicate if the mother has been exposed to any teratogenic medications (including steroids) before or during pregnancy (Yes, No). Pregnancies are considered unexposed to an MSDMD if the medication has not been used within 3 months prior to LMP or during pregnancy (except for mitoxantrone and cladribine, for which 6 months must be allowed).

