### 9.7.3 Analysis of primary objectives

With regard to objective #1, the descriptive statistics including the number of events (n) and prevalence (%) will be presented for each pregnancy outcome (i.e. serious adverse pregnancy outcome, elective TOPFA, MCA, stillbirth, and live birth) in each study cohort separately and also for the whole study population. Information on live births, stillbirths and TOPFAs will be included in the analyses of MCA, as approximately 10% of MCAs are detected in foetuses of TOPFA.

With regard to objective #2, the prevalence of the serious adverse pregnancy outcomes will be compared between the study cohorts using log-binomial regression. Two models, base and adjusted, will be used in these comparisons. The base model will be adjusted for the following design variables and *a priori* likely confounders: country, year of pregnancy outcome, maternal age at LMP, number of previous pregnancies, any chronic diseases, and exposure to any teratogenic medications including steroids.

The adjusted model will be built using a variable selection procedure (Bursac et al. 2008). Candidate covariates for the adjusted model will be those in the base model and the following additional ones: university hospital district, pre-pregnancy weight, pre-pregnancy BMI, number of previous abortions, smoking status during pregnancy, number of foetuses in pregnancy (single vs. multiple), time since MS diagnosis and duration of MS treatment as available in the data sources. Variable selection starts by applying first the unadjusted model and proceeds as follows:

1. Each candidate covariate will be considered a potential confounder if the univariate association between the covariate and the serious adverse pregnancy outcome, tested with the Wald test for logistic regression with *P*-value cut-point of 0.25.
2. All candidate covariates identified as potential confounders in step 1 will be added simultaneously to the model. After this, additional covariates not identified as potential confounders in step 1 will be added to the model one at a time and the model fit comparing each null vs alternative model will be assessed by the likelihood-ratio test. Variables in the alternate model will be retained at a likelihood ratio test of *P*-value <0.1.

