C	
Medicinal products, which by their pharmacological effects have caused or must be suspected of causing, disturbances in the reproductive process that may involve risk to the foetus without being directly teratogenic. If experimental studies in animals have indicated an increased occurrence of foetal injuries or other disturbances of the reproductive process of uncertain insignificance in humans, these findings are to be stated for drugs in this category.

D	
Medicinal products, which have caused an increased incidence of foetal malformations or other permanent damage in humans or which, on the basis of e.g. reproduction toxicity studies, must be suspected of doing so. This category comprises drugs with primary teratogenic effects that may directly or indirectly have a harmful effect on the foetus.

[figure not shown]
In this study, the following drugs (ATC codes) from categories C and D will be included in this study as potentially teratogenic drugs or teratogenic drugs.

	ATC codes						
Potentially teratogenic drugs – risk category C	A01AB11	A01AC01	A02BC02	A03AB02	A03FA01	A04AA03	A04AD12
	A05AA02	A07DA03	A07EA02	A07EA06	A10BB01	A10BB07	A10BB12
	A10BG02	A10BG03	A10BH01	A10BX02	A10BX03	A11HA30	B01AC06
	B01AC11	B01AC30	B01AD02	B01AD07	B01AD11	B01AE07	B03XA01
	C01BC03	C01BC04	C01BD01	C01BD05	C01CA04	C01CX08	C01EA01
	C02AC05	C03AA03	C03BA11	C03CA01	C03EA01	C04AD03	C07AA03
	C07AA05	C07AA07	C07AB02	C07AB03	C07AB05	C07AB07	C07AB09
	C07AG01	C07AG02	C07FB02	C08CA01	C08CA02	C08CA03	C08CA05
	C08CA06	C08CA07	C08CA13	C08DA01	C08DB01	C08DB01	C10AA03
	C10AA04	C10AA07	C10AB02	C07AB09	C07AG01	C07AG02	C10AB04
	C10AB05	D01AA02	D01AC07	D01AC08	D01AE16	D05AX03	D05AX52
	D06BB03	D06BB04	D07AB01	D07AB02	D07AB08	D07AC01	D07AC03
	D07AC13	D07AD01	D07BC01	D07CC01	D07XC01	D08AG02	D10AD01
	D10AD03	D11AH01	D11AX01	D11AX18	G01AF08	G02AB01	G02BB01
	G02CB03	G03AA11	G03AA12	G03AA13	G03AB03	G03AB05	G03AB06
	G03AC01	G03AC03	G03AC08	G03AC09	G03CX01	G03DA02	G03FA01
	G03FA12	G03FA17	G03FB05	G03FB06	G03GA01	G03AA07	G03AA09
	G03AA10	G03GA01	G03GB02	G03HB01	H01CA02	H01CB02	H01CB03
	H01CC02	H02AA02	H02AB01	H02AB02	H02AB04	H02AB06	H02AB07
	H02AB08	H03BB01	H05AA02	J01CA08	J01EA01	J01EE01	J01EE02
	J01FA09	J01FA15	J01GB01	J01MA01	J01MA02	J01MA06	J01MA12
	J01MA14	J01XC01	J01XE01	J01XX08	J02AB02	J02AC01	J02AC02
	J02AC03	J02AX04	J04AB02	J04AB04	J05AB01	J05AB11	J05AE02
	J05AE03	J05AE07	J05AF01	J05AF05	J05AF06	J05AF08	J05AR01
	J07BA02	J07BK01	L01XE01	L01XE06	L01XX19	L01XX23	L02AB01

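### The base-model teratogen flag gives category C and category D drugs one value, and its contraceptive codes are recorded in Sweden and Norway but mostly not in Finland

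*Protocol*

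**What the plan says.** Section 9.4 (exposure to any teratogenic medications) sets the scope: "In this study, drugs from categories C and D will be included as potentially teratogenic drugs or teratogenic drugs". One binary variable is then made from them, recording "if the mother has been exposed to any teratogenic medications (including steroids) before or during pregnancy (Yes, No"). The codes are written out in Annex 3, so their content is already fixed in the protocol.

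Annex 3 separates the two categories. Category D covers drugs that have caused, or must be suspected of causing, malformations or other permanent damage. Category C covers drugs that "may involve risk to the foetus without being directly teratogenic".

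Section 9.7.3 places the variable in the base model for the primary comparisons, among the likely confounders chosen in advance: "any chronic diseases, and exposure to any teratogenic medications including steroids".

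The data come from the prescription registers in section 9.3.1.1. Finland holds reimbursed purchases: "This excludes, for instance, most contraceptives". For the other two countries: "In SWE and NOR, all prescribed medicines purchased in community pharmacies are included irrespective of reimbursement status". The Finnish Drugs and Pregnancy Project (DPP) is narrower still in time: "Drug purchases are recorded covering a time period from one month prior to pregnancy to the end of pregnancy in the DPP". Table 2 also names the Finnish prescription register as a separate exposure source.

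**The concern.** A covariate controls confounding only if its value means the same thing for each pregnancy and tracks the risk it stands for. This flag has two weaknesses.

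First, it equates drugs with different risk. A pregnancy with a category D antiepileptic (N03AG01) and one whose only listed purchase was a contraceptive or a topical product both score Yes.

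Second, list C includes codes that the three registers do not record alike: G03AA07 and G03AA09 to G03AA13, G03AB03, G03AB05, G03AB06, G03AC01, G03AC03, G03AC08, G03AC09 and G02BB01. Annex 3 gives codes without names. That these are hormonal contraceptives follows from the ATC system, which the protocol uses throughout.

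At stake is the primary RR for cohort 1 against cohorts 3 and 4. The model would appear adjusted for teratogenic co-medication while confounding by category D drugs was only partly removed, and the flag's coefficient would average over different definitions by country.

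**Working it through.** **Yardstick from the plan.** Section 9.5 has 294 pregnancies in cohort 1, 1270 in cohort 3, baseline prevalence 7.3%, 80% power and 5% two-sided significance. Solve for RR in

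1.96·√[p̄(1−p̄)(1/294+1/1270)] + 0.842·√[p1(1−p1)/294 + p0(1−p0)/1270] = p1−p0, with p0 = 0.073, p1 = RR·p0 and p̄ the pooled prevalence.

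This gives RR 1.717 (1.720 with p0 = 24/331); the plan states 1.72. That figure is not in dispute. The plan gives no prevalence for the flag, so steps 2 to 4 rest on labelled assumptions.

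**Step 1: meaning by country.** Take a woman whose only listed purchase in the window is a contraceptive.

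| Country | Register content | Flag |
|---|---|---|
| Finland | reimbursed purchases; most contraceptives absent | usually No |
| Sweden, Norway | all prescribed pharmacy purchases | Yes |

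Sweden and Norway supply 482 + 412 = 894 of 1671 planned pregnancies (53.5%). Suppose 30% are flagged through other category C drugs, and 20% to 80% bought a contraceptive in the window, independently (assumptions). Finland shows 30%; Sweden and Norway show 1 − 0.8×0.7 = 44% to 1 − 0.2×0.7 = 86%. A country main effect shifts baseline risk. It does not restore a common meaning to a flag that has one coefficient for all countries.

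**Step 2: share flagged Yes.** Assume a constant monthly probability m of buying any listed drug, a look-back of w months before LMP, and 9 months of pregnancy: share = 1 − (1−m)^(w+9).

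| m | w = 3 | w = 60 |
|---|---|---|
| 1% | 11% | 50% |
| 2% | 22% | 75% |
| 5% | 46% | 97% |
| 10% | 72% | about 100% |

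The share is undetermined without the purchase rate and the window.

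**Step 3: what the coefficient reflects.** Set the study-drug codes aside (see the last paragraph). Assume 3% of pregnancies have a category D co-exposure, and read the 3-month shares in step 2 as category C purchase. The category D share of the Yes group is d = 0.03/(0.03 + 0.97×share):

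- share 11%: 0.03/0.1367 = 22%
- share 22%: 0.03/0.2434 = 12%
- share 46%: 0.03/0.4762 = 6%

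If category D carried RR 3 and category C none (assumptions), the flag would show about 1 + 2d, that is 1.44, 1.25 or 1.13. Even with a short window, category D is a minority of the Yes group and its risk is largely averaged away.

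**Step 4: effect on the primary RR.** If category D drugs were not adjusted for at all, the confounding factor would be [1 + a(R−1)]/[1 + b(R−1)], with prevalence a in one cohort, b in the other, and drug risk R (all assumed):

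- a = 6%, b = 3%, R = 2: 1.06/1.03 = 1.03
- a = 6%, b = 3%, R = 3: 1.12/1.06 = 1.06
- a = 6%, b = 2%, R = 3: 1.12/1.04 = 1.08

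The factor is therefore about 3% to 8%, and nil if the prevalences are equal. Because the flag removes part of it, these are upper figures for each scenario.

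**Separate matter, kept out of the arithmetic.** List D also contains L03AB07 and L03AB08, which the protocol's front table gives as the study drugs: "Interferon (IFN)- $\beta$ -1a (L03AB07) IFN- $\beta$ -1b (L03AB08"). While they stay on the list, cohort 1 is Yes by construction (except pregnancies exposed only to L03AB13, which is not listed) and step 3 does not describe the variable as written. Removing them would leave the C/D merger and the contraceptive mismatch in place.

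**The case against.** Pooling C and D is deliberate and disclosed: the text calls the drugs potentially teratogenic or teratogenic. The composite includes stillbirth, so drugs that may harm the foetus without causing malformations are relevant. This stands, and it argues against dropping category C or limiting category D to first-trimester use. It does not argue for giving both one coefficient.

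The length of the look-back is ordinary SAP content. This also stands: its absence alone is not the point. The contraceptive mismatch arises under any window in which contraceptives are bought.

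The base model adjusts for country, year and chronic disease (epilepsy is in Table 4), and sections 9.4 and 9.7.1 acknowledge that covariates depend on what each register holds. This helps in part, but chronic disease is itself one yes/no flag over all Table 4 conditions, and country adjustment fails for the reason in step 1.

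A reader might go further and infer that a contraceptive purchase at any time in the past counts, that most women in Sweden and Norway are Yes, or that category D users are only 3% to 4% of the Yes group. The documents do not support these as facts. The word before has no stated limit. The only window in that paragraph (three months, six for two drugs) is for MSDMDs, and a lifetime look-back is stated for chronic diseases only. The Swedish register dates from 2005 and the Swedish study period from 1 July 2005, so early pregnancies there have little recorded history on any reading. No Yes share is given anywhere.

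**Conclusion.** The point holds as a defect of definition with a modest expected effect. The documents alone establish that one value covers categories that Annex 3 distinguishes, that the flag is in the base model, and that the Finnish register lacks most contraceptives while the Swedish and Norwegian registers capture them. The covariate therefore differs in meaning across countries, and its coefficient can mainly reflect category C use.

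The size is assumption-based: a Yes share of about 11% to nearly 100% over the windows and purchase rates tried, and roughly 3% to 8% on the primary RR if category D use differs between cohorts as assumed. Against a minimum detectable RR of 1.72 that is small. It could matter for interpreting an RR near 1, but the documents give no basis for saying that the primary comparison is seriously biased, or in which direction. The change should be made because it is cheap and because the model would otherwise claim an adjustment that it only partly delivers.

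**What to change.** - Remove the hormonal contraceptive codes (G03AA, G03AB and G03AC codes, G02BB01) from the Annex 3 list used for this covariate.
- Replace the single flag with separate indicators for (i) category D drugs other than MSDMDs, (ii) systemic steroids, and (iii) the remaining category C drugs.
- State one look-back window before LMP that all three registers can supply, and which Finnish source supplies it. The DPP reaches back one month, while the Finnish prescription register named in Table 2 may reach further.

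The cost is a revision of Annex 3 and one derivation, with no new data. The flag becomes three terms, so the covariate-to-outcome limit in section 9.7.3 must be watched. At 7.3%, cohorts 1 and 3 give 1564 × 0.073 ≈ 114 events, or about 11 covariates at 1 per 10; at 3% prevalence it would be 47 events and 4 covariates. If that binds, the remaining category C indicator is the natural one to omit.

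The main downside is precision. At the assumed 3%, category D covers about 47 of 1564 pregnancies, with about 3 events at 7.3%. Its coefficient will be imprecise and the log-binomial fit may be unstable, so it should serve for adjustment and not be interpreted on its own.

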#### **Potential confounding factors and effect modifiers:**

The following confounding factors and effect modifiers will be taken into account in the analyses according to availability and available time period from each register source: any chronic diseases, exposure to any teratogenic medications including steroids, country of residence of the mother, university hospital district, maternal age at LMP, year of pregnancy outcome, pre-pregnancy weight, pre-pregnancy BMI, number of previous pregnancies, time since MS diagnosis, duration of MS treatment, number of previous abortions, smoking status during pregnancy and number of foetuses in the pregnancy (single or multiple).

## 9.5 Study size

Based on the feasibility study (cf. Annex 1) it is estimated that a total of 1671 MS pregnancies would be available for the current study from FIN, SWE and NOR. This total sample size was estimated as follows: In FIN 433 MS pregnancies were observed between 1 January 1996 and 31 December 2010 of which 86 were in 2010. For the actual study, data from FIN from 1 January 2011 to 31 December 2014 will also be used, and therefore the total number of available MS pregnancies was estimated to be 777 (433 + 4\*86, where 86 is the number of MS pregnancies in 2010). In SWE 329 MS pregnancies were observed during the time period 1 July 2005 – 31 December 2011 (329/6.5 years = 51 per year). Because the study period in SWE is from 1 January 2005 to 31 December 2014, the estimated number of MS pregnancies in SWE is 482 (329 + 3\*51). In NOR, 330 MS births were expected to occur in the time period 1 January 2004 – 31 December 2014, which was estimated to be 80% of all MS pregnancies excluding terminations of pregnancies. The number of MS pregnancies available in the study from NOR was thus estimated to be 412 (330/0.8). The total number of 1671 MS pregnancies available for the study is obtained as the sum of these estimated numbers (777 + 482 + 412).

From the 433 MS pregnancies in FIN, 102 (24%) and 331 (76%) were identified as exposed and unexposed to any MSDMD, respectively (in SWE, the proportion of unexposed to any MSDMDs was 77%). Furthermore, of the 433 MS pregnancies in FIN, 95 (22%) and 338 (78%) were identified as exposed and unexposed to IFN- $\beta$  regardless of exposure to other MSDMDs, respectively (personal communication with [name], THL, 15 May 2014). Based on these numbers, it was estimated that 76% (= 331/433) of all MS pregnancies will be unexposed to any MSDMD and 78% (= 338/433) of all MS pregnancies will be unexposed to IFN- $\beta$  (regardless of exposure to other MSDMDs). Based on a systematic review of MSDMD usage (La Mantia et al. 2014), it was estimated that 80% of those identified as exposed to IFN- $\beta$  would not be using other MSDMDs (368\*0.8 = 294). Table 5 presents the study population size by exposure to IFN- $\beta$  based on these assumptions.

The estimated background prevalence for the composite endpoint of serious adverse pregnancy outcome, consisting of TOPFAs, live births with MCA and all stillbirths, was 6.5% (personal communication with [name], THL, 15 May 2014) and 7.3% (= 24/331, based on the feasibility study in Finland, cf. Annex 1) in women with MS unexposed to IFN- $\beta$  (regardless of exposure to other MSDMDs) and unexposed to any MSDMD, respectively. Because these numbers best correspond to the study setting, they were taken as the most relevant baseline prevalences of serious adverse pregnancy outcomes in the sample size calculations. Lower outcome prevalences were investigated to test how sensitive the findings of minimum detectable effect sizes are to these assumptions. For comparison, in the Finnish feasibility study the prevalence of serious adverse outcomes was 3.7% = (38384/1031778) among all women, and according to EUROCAT 2015, the prevalence of malformation outcome among all women in the EU is 2.6%. The anticipated sample sizes in study cohorts 1-6 are:

- Cohort 1: 294 (80% of 368) for MS pregnancies exposed only to IFN- $\beta$ .
- Cohort 2: 368 (22% of 1671) for MS pregnancies exposed to IFN- $\beta$  regardless of exposure to other MSDMDs.
- Cohort 3: 1270 (76% of 1671) for MS pregnancies unexposed to any MSDMD.
- Cohort 4: 1303 (78% of 1671) for MS pregnancies unexposed to IFN- $\beta$ .
- Cohort 5: 33 (Cohort 4 size – Cohort 3 size = 1303 – 1270 = 33) for MS pregnancies exposed to MSDMDs except IFN- $\beta$  or glatiramer acetate (Copaxone®) or dimethyl fumarate (Tecfidera®).
- Cohort 6: Approximately 2.9 Million pregnancies for women from the general population in FIN, SWE and NOR without MS diagnosis based on the based on the feasibility study (cf. Annex 1).

With these sample sizes and baseline outcome prevalence, the minimum detectable effect size between the MS women exposed to IFN- $\beta$  only (cohort 1) vs. MS women unexposed to any MSDMDs (cohort 3) is 1.72 in terms of RR using 80% power and a 5% two-sided significance level. If the background prevalence calculated among MS pregnancies unexposed to any MSDMD's would be closer to that in the whole population, e.g. 6%, 5%, 4% or 3%, the respective minimum detectable effect sizes would be 1.81, 1.91, 2.04, and 2.23. Regarding the comparison of a composite serious adverse pregnancy outcome between women with MS exposed to IFN- $\beta$  only (cohort 1) vs. unexposed to IFN- $\beta$  regardless of exposure to other MSDMDs (cohort 4), the minimum detectable effect size (RR) is approximately 1.77. Regarding the comparison of the composite serious adverse pregnancy outcome between women with MS exposed to IFN- $\beta$ s regardless of exposure to other MSDMDs (cohort 2) vs. unexposed to any MSDMD (cohort 3), the minimum detectable effect size (RR) is approximately 1.66.

The sample size calculations were performed using the `bpower` function of the R programming language (<http://www.r-project.org>).

**Table 5: The estimated numbers of all MS pregnancies and MS pregnancies unexposed to IFN- $\beta$ s available for the study during the study period by country.**

Country and study period		ALL MS Pregnancies	MS Pregnancies unexposed to IFN- $\beta$ s 
Country	Study period	Number of pregnancies	Number of pregnancies
Finland	1 Jan 1996 – 31 Dec 2014	777 	606 
Sweden	1 Jul 2005 – 31 Dec 2014	482 	376 
Norway	1 Jan 2004 – 31 Dec 2014	412 	321 
TOTAL		1671	1303

1) Estimated as 433 from time period 1 Jan 1996 – 31 Dec 2010 plus 4\*86 MS pregnancies from four additional years 2011 – 2014 where 86 denotes the number of MS pregnancies in 2010

2) Estimated as 329 MS births from Jul 2005 – 31 Dec 2011 plus (329 / 6.5) MS births from three additional years 2012 – 2014.

3) Estimated as 330 MS births from 1 Jan 2004 – 31 Dec 2014 divided by (1-0.2) where 0.2 denotes the estimated abortion prevalence

4) Estimated as the number of ALL MS PREGNANCIES x 78% where 78% denotes the estimated proportion of MS pregnancies unexposed to IFN- $\beta$  regardless of exposure to other MSDMDs

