### 9.7.1 Population description

The study population consists of pregnant women with MS. A pregnancy event refers to terminations of pregnancy, spontaneous abortions, ectopic pregnancies, stillbirths and live births. The pregnancy event is considered as the experimental unit in this study. One woman may have several pregnancy events during the study period and all pregnancy events are included in the analysis.

The characteristics of all pregnancies are to be described with n, mean, median, standard deviation (SD), minimum, maximum and inter-quartile range for continuous variables and with n and percentage (%) for categorical variables. These population characteristics are to be presented for each study cohort separately and also for the whole study population. The following variables are to be included in the population description as available from the different countries:

- Country, university hospital district,
- Duration of MS treatment,
- Time since MS diagnosis,
- Year of pregnancy outcome,
- Maternal age at LMP,
- Pre-pregnancy maternal weight,
- Pre-pregnancy maternal BMI,
- Any chronic diseases during or before pregnancy,
- Exposure to any teratogenic medications (including steroids) during or before pregnancy,
- Number of previous pregnancies,
- Number of previous abortions,
- Smoking status during pregnancy and
- Number of foetuses in pregnancy (single, multiple).

Confounding factors and effect modifiers will be taken into account in the analyses according to availability and available time period from each register source.

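### The two baseline rates behind the primary minimum detectable effects do not fit together, the Norwegian count does not match the primary denominator, and repeat pregnancies are not allowed for; the shifts are small and go both ways

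*Protocol*

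**What the plan says.** **Baselines.** Protocol 9.5 gives two background prevalences of the serious adverse pregnancy outcome and states that both were used in the sample size calculations. For women with MS unexposed to IFN-beta (cohort 4), the rate for TOPFAs, "live births with MCA and all stillbirths, was 6.5" per cent, is cited to a personal communication of May 2014. For women unexposed to any MSDMD (cohort 3) it is "7.3% (= 24/331, based on the feasibility study in Finland, cf. Annex 1").

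**Where the groups come from.** The same section splits 433 Finnish MS pregnancies in two ways: 331 unexposed to any MSDMD, and "78% (= 338/433) of all MS pregnancies will be unexposed to" IFN-beta. Table 1 (section 8) defines cohort 4 as cohort 3 plus women exposed only to other MSDMDs.

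**Stated MDEs.** Cohort 1 (294) vs cohort 3 (1270) is given as RR 1.72, "using 80% power and a 5% two-sided significance level". For cohort 1 vs cohort 4 (1303), "the minimum detectable effect size (RR) is approximately 1.77".

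**Norway.** The text of 9.5 scales up 330 births, "which was estimated to be 80% of all MS pregnancies excluding terminations of pregnancies", to 412. Footnote 3 to Table 5 explains the same factor differently: "where 0.2 denotes the estimated abortion prevalence". Table 6 (9.7.2) sets the denominator of the primary composite as elective terminations plus births.

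**Unit of analysis.** Section 9.7.1: "One woman may have several pregnancy events during the study period and all pregnancy events are included in the analysis". Section 9.7.3 specifies log-binomial regression, and 9.5 used the R function bpower on pregnancy counts.

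**The concern.** A group cannot have fewer events than a subgroup of itself. The 331 pregnancies with 24 events are part of the 338, yet 6.5% of 338 is about 22 events. Both rates feed a primary MDE, and 1.72 is repeated in the abstract.

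Two further inputs affect the same figures. If the pregnancies added for Norway are neither births nor terminations, they can never enter the primary analysis, although they are part of the 1671 from which every cohort size is derived. And when a woman contributes several pregnancies, a calculation for independent binomials overstates the information if outcomes recur within women; confidence intervals that ignore this would be too narrow.

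At stake is the accuracy of the sensitivity claimed for the two primary comparisons, which section 9.9 says the study has been powered for.

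**Working it through.** **Formula.** Two proportions, pooled variance under the null, two-sided 5%, no continuity correction (the bpower form). With p1 = RR × p0 and pm = (n1·p1 + n0·p0)/(n1 + n0):

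z = [(p1 − p0) − 1.96·√(pm(1 − pm)(1/n1 + 1/n0))] / √(p1(1 − p1)/n1 + p0(1 − p0)/n0), power ≈ Φ(z).

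**1. The protocol's own figures**
- Cohort 1 vs 3: n = 294 and 1270, p0 = 0.073, RR = 1.72. p1 = 0.1256, pm = 0.0829, null SE 0.01784, alternative SE 0.02066. z = (0.05256 − 1.96 × 0.01784)/0.02066 = 0.851, power 80.3%. Solving for exactly 80% gives RR 1.717 (1.720 with 24/331 unrounded).
- Cohort 1 vs 4: n = 294 and 1303, p0 = 0.065. Solving gives RR 1.767; stated 1.77.

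Both reproduce, so the fault is in the inputs and not in the calculation.

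**2. Consistency of the baselines**
- 0.065 × 338 = 21.97, so 6.5% corresponds to 22/338 (6.51%; 23/338 would be 6.80%). The count of 22 is back-calculated and is not printed in the protocol.
- 24 events in the 331 imply at least 24 in the 338: 24/338 = 7.10%.
- Rounding does not help. For 24 events to round to 6.5%, the group must exceed 24/0.0655 = 366.4 pregnancies; there are 338.

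| Assumption | Comparison | Baseline | MDE | Stated |
|---|---|---|---|---|
| 24 events in the 331, none in the other 7 | 1 vs 4 | 24/338 = 7.10% | 1.73 | 1.77 |
| one event in the other 7 | 1 vs 4 | 25/338 = 7.40% | 1.71 | 1.77 |
| two events in the other 7 | 1 vs 4 | 26/338 = 7.69% | 1.69 | 1.77 |
| 22 events in the 338, all in the 331 | 1 vs 3 | 22/331 = 6.65% | 1.76 | 1.72 |
| 22 events in the 338, 21 in the 331 | 1 vs 3 | 21/331 = 6.34% | 1.78 | 1.72 |

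So 1.73 is an upper limit for cohort 1 vs 4, and 1.76 a lower limit for cohort 1 vs 3.

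**3. Norway**
- 330/0.8 = 412, so 412 − 330 = 82 pregnancies are added. On the text of 9.5 these are neither births nor terminations and lie outside Table 6.
- 1671 − 82 = 1589. Cohort 1: 0.8 × 0.22 × 1589 = 280. Cohort 3: 0.76 × 1589 = 1208. At 7.3% the MDE is 1.74, and power at RR 1.72 is 78.5%.
- This is an upper limit for this correction. Norwegian terminations from gestational week 12 are registered and count in Table 6, but births alone leave them out.

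**4. Repeat pregnancies**

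The documents give neither the number of pregnancies per woman nor the recurrence. With assumed design effects of 1.06 to 1.13, dividing 294 and 1270 by the design effect gives an MDE of 1.74 to 1.77 for cohort 1 vs 3. Standard errors that ignore this would be too small by a factor of √1.06 = 1.03 to √1.13 = 1.06.

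**The case against.** **Different sources.** The 6.5% is cited to a personal communication of May 2014 and 24/331 to the feasibility report of December 2013. Events could have been ascertained differently in two extractions. This stands as a possibility, and it is why the two rates cannot be called impossible without qualification. But 9.5 presents the 338 as a split of the same 433 pregnancies, cites that split to the same personal communication as the 6.5%, and mentions no second extraction.

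**Direction.** If 24/331 is right, the stated 1.77 is conservative and power for cohort 1 vs 4 was understated. This stands.

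**Norway.** Footnote 3 may mean induced abortions, and those from week 12 belong in the denominator. This stands in part: text and footnote disagree, and simply using 777 + 482 + 330 would also be a wrong count because it contains no Norwegian terminations.

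**Variance estimator.** The protocol announces a separate analysis plan, and standard errors are usually set there. That would dispose of a bare omission. Here, however, the protocol itself fixes the pregnancy as the unit, keeps all pregnancies of a woman, names the model, and states power from a method for independent observations. The size of the effect remains an assumption, and women who contribute to both compared cohorts could reduce it.

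**Materiality.** The restated values in the working run from 1.69 to 1.78, below the 1.81 to 2.23 that 9.5 already discloses for baselines of 6% down to 3%. All available pregnancies are used, so no recruitment target depends on them. This stands and limits the weight of the point.

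**Conclusion.** The point holds as an inconsistency of inputs. If both rates come from the same 433 Finnish pregnancies, 6.5% and 24/331 cannot both be right, and at least one primary MDE is misstated: cohort 1 vs 4 is at most 1.73 (stated 1.77) if 24 events stand, or cohort 1 vs 3 is at least 1.76 (stated 1.72) if 22/338 stands. The documents do not show which rate is wrong. The Norwegian count moves the cohort 1 vs 3 MDE to 1.74 at most; within-woman correlation would move it to about 1.74 to 1.77 under assumed design effects.

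A reader might infer that the study is underpowered, or that the inputs were chosen to flatter it. The documents support neither. The shifts go in both directions, raising 6.5% improves that MDE, and all of them stay within the sensitivity range the protocol already reports. Nor do the documents show that all 82 Norwegian pregnancies are ineligible, because footnote 3 leaves their nature open.

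**What to change.** 1. In 9.5, reconcile 6.5% with 24/331 against the feasibility data. Give numerator and denominator for both rates, or state that they come from different extractions. Restate the affected MDE in 9.5 and, if it is the 1.72, in the abstract.
2. Reconcile the text of 9.5 with footnote 3 to Table 5 on what the 20% represents. Base primary power on pregnancies in the Table 6 denominator; for Norway that means births plus registered terminations from week 12, not 330/0.8.
3. In 9.7.3, keep the log-binomial model and add that standard errors are clustered on the woman's study ID (GEE or sandwich). State the MDE with an explicit, labelled design effect.

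The cost is a few recalculated figures, one sentence on the variance estimator, and a query to the holder of the feasibility data. Cohort definitions, outcomes and data requests do not change.
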